### **11.3.9 Gonioscopy and Bim SR Implant Assessment**

Gonioscopy is performed to assess the inferior iridocorneal angle and the Bim SR implant in study visits during Cycle 1 and Cycle 2 for all patients, and during Cycle 3. Patients presenting with peripheral anterior synechiae (PAS) on gonioscopy at any time during the study will be presented in a listing with the time period in which it occurred.

If an implant is visible, visible implant size is to be recorded on eCRF as a percentage of the original material (0-25, 26-50, 51-75, 76-100, 101-125, 126-150, 151-200, >200). Number and percentage of patients with any implant visible during the study will be summarized in a tabular format. In addition, number and percentage of implants visible will also be summarized during each study period for Bim SR eye further breaking down by the categorical percentage visible of each implant. Also, the number and percentage of patients who have any implant(s) in contact with corneal endothelium at any visit within a cycle will be summarized by analysis cycle. Implant assessment will be presented as data listings displaying the location of implant (12 zones), status of contact with other implant(s), and status of contact with corneal endothelium for each patient.

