Efficacy: The primary efficacy analysis will be performed for patients in the intent-to-treat (ITT) population. The primary efficacy variable is IOP change from baseline and the primary time period is 24 weeks (measurements for the primary analysis are designated for the following timepoints: Weeks 4, 12, and 24).

IOP change from baseline will be analyzed using a mixed effect model for repeated measures (MMRM). The model will include IOP change from baseline as the response variable and treatment, visit, eye, baseline IOP, treatment-by-visit, treatment-by-baseline, treatment by eye, and visit-by-eyes interactions as covariates. Unstructured correlation for study visits and compound symmetry correlation for eyes will be used for repeated measures on the same patient; if the model fails to converge, multiple imputation (MI) will be implemented before MMRM. The mean difference between the Bimatoprost SR 15 µg eyes and SLT eyes (Bimatoprost SR 15 µg minus SLT) in the ITT population and the corresponding 95% confidence interval (CI) will be constructed at each visit. The noninferiority comparison for Bimatoprost SR 15 µg versus SLT at Weeks 4, 12, and 24 is the primary analysis. If the upper limit of the 95% CI is ≤ 1.5 mm Hg at all 3 visits, Bimatoprost SR 15 µg statistical noninferiority to SLT is considered demonstrated. In addition, Bimatoprost SR 15 µg is considered clinically noninferior to SLT if the upper limit of the 95% CI is ≤ 1.0 mm Hg at 2 out of the 3 visits of Weeks 4, 12, and 24.

Secondary efficacy variables to compare Bimatoprost SR eyes and SLT eyes include: time to initial use of nonstudy IOP-lowering treatment (as determined by the investigator); percentage of Bimatoprost SR and SLT eyes achieving $\geq 20\%$ reduction in IOP from baseline by visit; and IOP changes from baseline at Weeks 8, 15, and 20.

Safety: Safety analyses will be performed for patients in the Stage 1 and Stage 2 safety populations. Adverse events will be coded using Medical Dictionary for Regulatory Activities (MedDRA) nomenclature. The number and percentage of patients reporting treatment-emergent adverse events will be tabulated based on the system organ class and preferred term. Ocular safety variables will be tabulated by Bimatoprost SR or SLT eye. Nonocular safety variables will be summarized.

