 - a. Use of soft lenses should be discontinued at least 3 days prior to Baseline, and use of rigid gas permeable or hard contact lenses should be discontinued at least 1 week prior to Baseline
 - b. Use of soft lenses should be discontinued at least 3 days and use of rigid gas permeable or hard contact lenses should be discontinued at least 1 week prior to a scheduled study visit or Administration Day visit
 - c. Use of contact lenses of any kind should be discontinued for 1 week following any Bimatoprost SR (or Sham) administration
21. Central corneal thickness of < 480 or > 620 micrometers
22. Anticipated need for any incisional or laser ocular surgery during the study
23. History of anatomically narrow angle resulting in evidence of angle changes or any history of closed angle glaucoma. Note: historically narrow angled patients whose angle has been opened by cataract surgery or peripheral iridotomy may be eligible for enrollment if they have no evidence of angle abnormalities.
24. History or evidence of a peripheral iridotomy/iridectomy in the inferior iris

25. Any history of trabeculectomy or other types of glaucoma surgery, including a glaucoma seton or aqueous bypass stents
26. Peripheral anterior synechiae (PAS) in the inferior iridocorneal angle on gonioscopic examination at Screening
27. Visual field loss that, in the opinion of the investigator, is functionally significant (eg, split fixation, field defect within the central 10 degrees that is visually significant or likely to cause central visual impairment upon progression) or shows evidence of progressive visual field loss within the year prior to baseline (Note: Two visual fields are required for qualification, 1 performed within the 10 months prior to or at Screening, and 1 performed at baseline or during the washout period using the protocol-required testing method [see Procedure Manual]. The same test methodology should be used for all historical and study-related examination for a given patient.)
28. Evidence of macular edema during screening or in patient's medical history
29. Anticipated use of corticosteroids in either eye (except as described in Section 4.5.1 [Permissible Medications/Treatments]) or systemically during the study, or historical use prior to Baseline within:
 - 3 years: intraocular fluocinolone acetonide
 - 6 months: intraocular corticosteroid(s) other than fluocinolone; any injectable periocular or sub-Tenon's/subconjunctival corticosteroid

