Macroscopic Conjunctival Hyperemia Assessment: Macroscopic conjunctival hyperemia will be assessed using the appropriate assessment guide (see the Procedure Manual for further details).

Gonioscopy/Angle Assessment: Gonioscopic examination for eligibility at Screening (only) will be independently performed by 2 ophthalmologists as described in the Protocol Procedure Manual. The independent eligibility assessors should not share their assessments with each other until the assessment is recorded. The 2 ophthalmologists' independent eligibility assessments must confirm patient eligibility for participation in the study. Subsequent gonioscopic examinations will be performed by the study investigator. Using gonioscopy, the investigator will evaluate the inferior iridocorneal angle and the Bimatoprost SR implant.

Biomicroscopy: Biomicroscopic examinations will be performed using a slit lamp. The examinations will include evaluation of the condition of the eyelids, conjunctiva, cornea, AC (with Van Herick anterior chamber depth assessment at Screening only), iris/pupil, and lens (Lens assessment is performed using the modified AREDS procedure and is collected on dilated examination days through a dilated pupil, using the slit lamp biomicroscope. Please see the Procedure Manual for details).

Lens Assessment: Biomicroscopic findings will be evaluated for the presence and severity of nuclear, cortical, and posterior subcapsular lens opacities. See the Procedure Manual for further details.

Optic Disc Examination: The cup/disc ratio and presence of optic disc pathology will be determined using stereoscopic evaluation.

Dilated Ophthalmoscopy: The stereoscopic fundus assessments should be conducted through a dilated pupil. The examinations will include evaluation of the macula, vitreous, and retina.

Specular Microscopy: Endothelial cell density will be assessed using specular microscopy performed on the central cornea at all sites. The determination of central endothelial cell density for study entry as well as study visit measures will be determined by the Reading

Center. See the Procedure Manual for further details. The same instrument should be used throughout the study for a given patient. Qualification will remain valid for 1 year after Screening in patients who are not enrolled at the time of Screening, if in the investigator’s opinion there have been no clinically significant changes occurring in the eyes (eg, ocular surgery) during that time.

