7.3.4 Safety Analyses

Safety analyses will be performed for patients in Stage 1 and in Stage 2 safety populations. The Medical Dictionary for Regulatory Activities (MedDRA) nomenclature will be used to code adverse events. Adverse events will be coded from the verbatim text into preferred term and system organ class (SOC). The number and percent of patients reporting treatment emergent adverse events will be tabulated based on the primary SOC and preferred terms. Summary tables will be generated for all adverse events regardless of causality as well as treatment-related adverse events for the entire study and by treatment cycle. Other safety variables include vital signs (blood pressure, pulse rate, and temperature) and pregnancy test results. Ocular safety will be evaluated through assessment of visual acuity and visual field, evaluation of macroscopic bulbar conjunctival hyperemia and iris color, assessment of endothelial cell density and corneal thickness, IOP measurement, and biomicroscopic and ophthalmoscopic examinations (including gonioscopy with Bimatoprost SR implant assessment, optic disc examination, and dilated fundus examination).

Ocular adverse events and safety variables will be summarized by Bimatoprost SR or SLT eye, and nonocular safety variables will be summarized by patient. A separate summary will be provided for safety events occurring after nonstudy IOP-lowering medication has been initiated.

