8.4.3.5 Cycle 1: Day 4 and Week 2 (Cycle 1 Phone Calls)

On Cycle 1 Day 4 and Cycle 1 Week 2, the patient will be contacted by telephone to collect the following:

- Collection of adverse events
- Collection of concomitant medications and procedures

If the patient reports symptoms or findings of concern in the Day 4 or Week 2 phone call (including but not limited to photophobia, blurred vision, eye pain, vitreous floaters), the investigator must bring the patient in for ophthalmic examination.

8.4.3.6 Cycle 1: Weeks 4, 8, 12, and 15

The following procedures are performed at Weeks 4 (\pm 4 days), 8 (\pm 4 days), 12 (\pm 4 days), and 15 (\pm 4 days):

- Collection of adverse events
- Collection of concomitant medications and procedures
- Vital signs (at rest \geq 5 minutes)

The following procedures should be performed in both eyes (procedures in bold should be done in the order shown):

- **Pre-Hour 0 examinations** (may be performed in any order before Hour 0 IOP):
 - Macroscopic conjunctival hyperemia assessment (The examination may also include, [REDACTED])
 - Best-corrected visual acuity
- **Intraocular pressure measurement at Hour 0**
- **Non-contact examinations:** The following may be performed in any order, at any time before gonioscopy (including prior to Hour 0 IOP):
 - Macroscopic iris color assessment (Weeks 4 and 12 only)
 - Manifest refraction (Week 12 only)
 - Specular microscopy (Weeks 4 and 12 only)
 - Biomicroscopy (The examination may also include, [REDACTED])
- **Intraocular pressure measurement at Hours 2 and 8** (at selected sites in consenting patients; Week 12 only)
- **Gonioscopy/angle assessment** (The examination will also include, [REDACTED]). Perform gonioscopy at least 2 hours prior to H8 IOP measurement at Week 12.)
- Pachymetry (may be done any time after gonioscopy; Weeks 4 and 12 only)
- **Pupil dilation** (Week 12 only) (post dilation examinations below may be performed in any order)
 - Dilated ophthalmoscopy (Week 12 only)
 - Optic disc examination (Week 12 only)

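### Peripheral anterior synechiae are only listed by patient, not tabulated by Bim SR and SLT eye as the protocol says for ocular safety variables

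*SAP*

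**What the plan says.** **Protocol.** Section 7.3.4 names gonioscopy, with the implant assessment, among the ocular safety evaluations and adds: "Ocular adverse events and safety variables will be summarized by Bimatoprost SR or SLT eye". The Protocol Summary, under Safety, makes the same commitment: "Ocular safety variables will be tabulated by Bimatoprost SR or SLT eye". Section 6.2 describes the follow-up examination: "Using gonioscopy, the investigator will evaluate the inferior iridocorneal angle and the Bimatoprost SR implant". Exclusion criterion 26 in section 4.4, which applies to both eyes, bars: "Peripheral anterior synechiae (PAS) in the inferior iridocorneal angle on gonioscopic examination at Screening".

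**SAP.** Section 11.0 includes the gonioscopy and angle assessment in its list of ocular safety evaluations. It plans summaries of ocular safety assessments for the whole study and for each analysis cycle, based on the treatment each eye received. Section 11.3.9 then covers gonioscopy itself: "Gonioscopy is performed to assess the inferior iridocorneal angle and the Bim SR implant in study visits during Cycle 1 and Cycle 2". For PAS it specifies: "Patients presenting with peripheral anterior synechiae (PAS) on gonioscopy at any time during the study will be presented in a listing", which also gives the time period. The same section asks for numbers and percentages for implant visibility, visible implant size and contact with the corneal endothelium. It asks for none for PAS.

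**The concern.** Safety compared with SLT is half of the study objective (Protocol 2.1, SAP 5.1). SLT is applied around 360 degrees, and the implant is evaluated by gonioscopy together with the inferior angle, so a finding in the angle bears on both treatments. PAS is the only angle finding named in SAP 11.3.9 that can occur in either eye. The items that section does tabulate describe the implant and so have no counterpart in the SLT eye.

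A listing of patients gives no rate. If it does not show the eye, it does not say which treatment the finding belongs to. In a paired-eye trial every patient with PAS contributes one Bim SR eye and one SLT eye, so the patient is the wrong unit for this output.

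**Working it through.** No arithmetic in the plan bears on this point. The documents state no PAS rate and no precision target for it. The check is a comparison of texts, plus a count of scheduled examinations.

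1. **Is gonioscopy an ocular safety variable?** Yes, in Protocol 7.3.4 and again in SAP 11.0.

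2. **What output is promised for such variables?** Protocol 7.3.4 says a summary by treated eye, and the Protocol Summary says a tabulation by treated eye. SAP 11.0 adds the study periods: whole study and Analysis Cycles 1, 2 and 3.

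3. **What output does PAS get?** A listing of patients with the time period (SAP 11.3.9). That text mentions no eye, count, percentage or reference to Screening.

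4. **Is PAS treated like other eye findings?** No. In the SAP:
   - endothelial cell loss is given as number and percentage of patient-eyes by visit (11.3.5);
   - slit-lamp findings present after baseline but absent at baseline are given as number and percentage of eyes (11.3.7). The iris items there include posterior synechiae but not PAS;
   - categorical change in cup/disc ratio is given for each eye by visit (11.3.7);
   - lens opacity is given by visit and eye (11.3.8).

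5. **Are the examinations scheduled in both eyes?** Yes:
   - Weeks 4, 8, 12 and 15: 4 visits (Protocol 8.4.3.6);
   - Weeks 20, 24, 28 and 31: 4 visits (8.4.3.10);
   - Weeks 36, 40, 44, 47 and 52/Exit: 5 visits (8.4.3.14).

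   Total: 4 + 4 + 5 = 13 follow-up visits, or 13 × 2 = 26 eye examinations for a patient who attends all of them.

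6. **Is there another route to a by-eye table?** One. The adverse event definition in Protocol 9.1.1 is broad enough to cover a newly found sign. Ocular treatment-emergent events are tabulated per eye by system organ class and preferred term, overall and by period (SAP 11.1). A PAS finding enters that table only if the investigator reports it as an event, and Protocol 9.4 states that the primary investigator is unmasked.

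7. **Can new PAS be told from old?** In the inferior angle, yes: criterion 26 means that any inferior PAS seen later is new. Elsewhere in the angle it depends on what was recorded at Screening.

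Steps 1 to 3 show the shortfall against the protocol and against the SAP's own general rule. Step 6 shows that it is partly covered, by a route that depends on reporting.

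**The case against.** The other side has several fair points, and they limit how far the concern goes.

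- A reader might infer that PAS is never compared between the two eyes. The documents do not support that. A PAS reported as an adverse event enters the by-eye event tables, and SAP 11.1 speaks of comparing incidence across Bim SR and SLT eyes. This point stands, but it does not remove the gap. Slit-lamp findings can also be adverse events, and they still have their own by-eye tables.
- A reader might infer that the protocol promises a formal contrast for PAS. It promises a summary or tabulation by eye. It does not name PAS as a follow-up variable. The ocular safety outputs in SAP 11.3 are descriptive, with no paired test even for endothelial cell loss. A paired test for PAS alone would go beyond the plan.
- A reader might infer that PAS is looked for explicitly at each of the 13 visits. The protocol says that gonioscopy is done and that the inferior angle is evaluated. That this includes a PAS check is a reasonable inference from SAP 11.3.9, which expects to report PAS found at any time, but it is not stated visit by visit.
- A reader might infer that the listing mixes old and new PAS. This is weak. Follow-up gonioscopy is directed at the inferior angle, where PAS is excluded at entry, and criterion 23 bars a narrow-angle history with angle changes.
- SAP 4.0 places table and listing specifications in a separate document, which is not available here. That document may show the eye in the listing or contain a by-eye table. Only the SAP text can be judged.

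It can also be said that a complete listing discloses every case and that a reader could count them. That works only if the eye is shown, and it leaves to the reader a tabulation that the protocol assigns to the report.

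**Conclusion.** The concern holds in limited form. Followed as written, SAP 11.3.9 gives PAS a patient listing where the protocol calls for ocular safety variables to be tabulated or summarized by treated eye and SAP 11.0 calls for summaries by period. Between-eye information on PAS would then rest on adverse event reporting by an unmasked investigator.

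The size is one missing descriptive table for one examination finding. No efficacy result, error rate or power figure is affected. How many patients are concerned cannot be said, because no PAS rate is given.

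The conclusion assumes that the separate table specifications do not already contain a by-eye PAS table, and that PAS seen at gonioscopy is recorded for each eye. The case report form is not shown. The change is worth making because it brings the SAP into line with the protocol on a finding relevant to both treatments.

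**What to change.** In SAP 11.3.9:

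1. Add a table of the number and percentage of eyes with post-baseline PAS, by Bim SR eye and SLT eye, for the whole study and by analysis cycle. Use the Safety Population and the treatment-received convention of SAP 6.3 and 11.0.
2. Count as new any PAS not recorded in that eye at Screening. Inferior PAS is new by exclusion criterion 26.
3. Keep the listing and show the eye in it.

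No formal paired test and no breakdown by location in the angle is required.

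The cost is a few lines of SAP text, one descriptive table and one listing column. The gonioscopy is already scheduled in both eyes, so there is no added visit, procedure or site work, provided that PAS is recorded by eye.

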## 4.0 INTRODUCTION

This statistical analysis plan (SAP) provides a more technical and detailed elaboration of the statistical analyses of the efficacy and safety data as outlined and/or specified in the Study Protocol 192024-095 ([Amendment 3](#)). Specifications of tables, figures, and data listings (TFLs) are contained in a separate document. Additionally, if data are to be excluded from per-protocol analyses, a separate document will provide detailed rules for the data exclusion.

Study 192024-095 is a multicenter, paired-eye, randomized, efficacy evaluator-masked 14-month study conducted in 2 stages (Stage 1 and 2). The safety and intraocular pressure (IOP)-lowering effect of Bimatoprost SR (Bim SR) will be compared with selective laser trabeculoplasty (SLT) in open-angle glaucoma (OAG) or ocular hypertension (OHT) patients who are not adequately managed with topical medication for reasons other than medication efficacy (e.g., due to intolerance or nonadherence).

After the screening visit procedures, patients currently being treated with IOP-lowering medication(s) in either eye will begin washout of these medication(s) for a medication-dependent minimum washout period. The maximum washout period is 42 days. Baseline visit occurs after the washout period has been completed. To be eligible to participate in the study, at the Baseline visit, patients must have an Hour 0 IOP of  $\geq 22$  and  $\leq 34$  mmHg in each eye with a difference between the eyes of  $\leq 5$  mmHg. The eye with the higher IOP at Baseline will be assigned as the primary eye. If baseline IOP is the same in both eyes, the right eye will be the primary eye. The primary eye will be randomized to receive either Bim SR or SLT using a 1:1 ratio, stratified by:

- primary eye baseline IOP ( $\leq 25$  versus  $> 25$  mmHg)

and

- 

If the primary eye receives Bim SR, the contralateral eye will receive SLT. If the primary eye receives SLT, the contralateral eye will receive Bim SR.

The study is being conducted in 2 stages because the protocol was amended ([Amendment 2](#)) to reduce the number from 3 to 2 cycles of Bim SR administration, which allows for longer duration of efficacy follow up after the second administration:

- **Stage 1:** Bim SR 15  $\mu$ g vs SLT; 3 administration cycles for patients who were enrolled and reached the Week 32 administration visit prior to implementation of Protocol Amendment 2

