## 11.0 SAFETY ANALYSES

All safety analyses will be performed using the Safety Population. As indicated in [Section 6.5](#), safety data collected at Screening for eligibility assessment will not be analyzed.

Non-ocular safety assessments include: non-ocular adverse events (AEs), clinical laboratory, vital signs (blood pressure, pulse rate and temperature), and pregnancy test. Ocular safety will be evaluated through: ocular AEs, best corrected visual acuity, visual field examination, specular microscopy, macroscopic iris color assessment, macroscopic conjunctival hyperemia assessment, gonioscopy / angle assessment, biomicroscopy (using a slit lamp), lens assessment, optic disc examination, dilated ophthalmoscopy, pachymetry, and anterior segment-optical coherence tomography.

[REDACTED]

Unless otherwise stated, the last non-missing safety assessment before the SLT treatment (Day 1) will be used as the baseline for all analyses of that safety parameter.

Analysis study periods are defined as follows:

- **During the study:** Date of SLT treatment through Week 52/Exit visit/last study visit available.
- **Analysis Cycle 1:** SLT Treatment date (Day 1) through the second Bim SR implant date – 1. If the second Bim SR implant was not given to a patient, all safety assessments through Week52/Exit visit/last study visit available will be included in analysis cycle1.
- **Analysis Cycle 2:** Second Bim SR implant date through the third Bim SR implant date – 1. If the third Bim SR implant was not given to a patient, all safety assessments through Week52/Exit visit/last study visit available will be included in analysis cycle 2.
- **Analysis Cycle 3:** Third Bim SR implant date through Week 52/Exit visit/last study visit available. Note that only Stage 1 patients were eligible to receive third Bim SR implant.

All summaries will be based on the first treatment received in each eye (Bim SR or SLT), except one patient who received both SLT and Bim SR in the same eye (Safety assessment will be summarized in Bim SR). For non-ocular safety measures, overall summaries will be presented. For ocular safety assessments, summaries will be presented for the periods of during the study, Analysis Cycle 1, Analysis Cycle 2, and Analysis Cycle 3 as shown in Figure 11-1 below.

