### 11.3.5 Specular Microscopy

**Endothelial Cell Density:** Endothelial cell density average (cells/mm^2) will be assessed using specular microscopy performed on the central cornea of each eye at Screening, Week 4, Week 12, Week 24, Week 40, and Week 52/Exit.

Endothelial cell density at baseline (Screening) and raw values and their changes from baseline will be summarized descriptively by visit for each eye.

In addition, the number and percentage of patient-eyes that showed following

- beyond 200 cells/mm^2 increase
- within 200 cells/mm^2 increase
- within 200 cells/mm^2 decrease
- ≥ 10% loss
- ≥ 20% loss
- ≥ 30% loss
- ≥ 40% loss
- ≥ 50% loss
- ≥ 10% and < 20% loss
- ≥ 20% and < 30% loss
- ≥ 30% and < 40% loss
- ≥ 40% and < 50% loss

in endothelial cell density change from baseline will be summarized by visit for each eye. Percent change from baseline is defined as:  $100 \times (\text{At Visit ECD} - \text{Baseline ECD}) / (\text{Baseline ECD})$  where ECD = endothelial cell density. For the ECD decrease, the worst ECD assessment within the given analysis visit window (or analysis cycle) including unscheduled visits will be summarized by visit and by analysis cycle. For the ECD increase, the maximum ECD assessment will be summarized by visit and by

analysis cycle. Listings for patients with 20% or more central corneal endothelia cell density (CECD) loss at any visit will be provided.

**Coefficient of Variation Average (CVAVE):** Coefficient of variation average of raw data and changes from baseline will be summarized descriptively by visit for each eye.

**Pleomorphism Average (HEXAVE):** Pleomorphism average of raw data and their changes from baseline will be summarized descriptively by visit for each eye.

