#### **16.4 REPEATED OR UNSCHEDULED ASSESSMENTS OF SAFETY PARAMETERS**

For safety parameters, if a patient has repeated assessments before the SLT treatment, unless otherwise stated, the results from the latest non-missing assessment made prior to the SLT treatment will be used as baseline. If end-of-study assessments are repeated or if unscheduled visits occur, the last non-missing postbaseline assessment will be used as the end-of-study assessment for generating summary statistics. However, all postbaseline assessments will be used for safety evaluation, and all assessments will be presented in the data listings.

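### The per-cycle table of implant–endothelium contact in SAP 11.3.9 pools eyes with 4 to 13 scheduled looks, so its Cycle 1 and Cycle 2 percentages cannot be compared

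*SAP*

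**What the plan says.** **Contact table.** SAP 11.3.9 plans a count, with a percentage, of those "who have any implant(s) in contact with corneal endothelium at any visit within a cycle will be summarized by analysis cycle". One contact in a cycle counts the same as contact at every visit in it.

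**Visible implants.** The same section has one whole-study count, "Number and percentage of patients with any implant visible during the study will be summarized in a tabular format", and a per-period count, "number and percentage of implants visible will also be summarized during each study period for Bim SR eye". Location and contact status also go into listings. No by-visit implant table is described.

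**Cycle definition.** SAP 11.0 starts Cycle 1 on the day of SLT and ends it the day before the second implant. If there is no second implant, "all safety assessments through Week52/Exit visit/last study visit available will be included in analysis cycle1". Cycle 2 ends the day before a third implant; if there is none, "all safety assessments through Week52/Exit visit/last study visit available will be included in analysis cycle 2". Cycle 3 runs from the third implant to exit.

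**Comparison with another corneal measure.** In SAP 11.3.5 the worst cell density in each window, "including unscheduled visits will be summarized by visit and by analysis cycle". Corneal thickness (11.3.6), cup/disc ratio (11.3.7) and lens opacity (11.3.8) are also summarised by visit.

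**The concern.** The chance that an any-visit count is positive grows with the number of visits, and here that number depends on how many implants the patient received. The imbalance is built into the design. Stage 2 patients are planned for two implants, so a Cycle 2 running to Week 52 is their normal case. Patients who had not reached Week 16 when Amendment 3 took effect get no second implant but are followed to Week 52 (Protocol 5.9.1.5), which creates the long Cycle 1.

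The table bears on the issue that ended dosing. Protocol 1.3 attributes the stop to corneal adverse events after repeated 15 µg dosing, and Protocol 1.2.1 links the intolerance seen in monkeys to long-lasting contact between implant and endothelium. Two natural questions follow: is contact more common after the second implant, and does it last? A difference between cycles could come from the number of looks alone, and the row cannot separate a single contact from a persistent one.

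**Working it through.** **1. Check the schedule against the protocol's own total.** Protocol section 8 states a minimum of 20 visits for patients who complete all treatments. Screening, Baseline, Day 1, Day 4, Cycle 1 Day 2 (5); Weeks 4, 8, 12, 15 (4); Week 16 and Cycle 2 Day 2 (2); Weeks 20, 24, 28, 31 (4); Weeks 36, 40, 44, 47, 52 (5). Sum: 5 + 4 + 2 + 4 + 5 = 20. The total is reproduced.

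**2. Post-implant gonioscopy visits.** Protocol 8.4.3.6, 8.4.3.10 and 8.4.3.14 list gonioscopy at every one of their visits: 4 + 4 + 5 = 13.

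**3. Assign them to the SAP 11.0 cycles, follow-up to Week 52.**

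| Implants received | Cycle 1 | Cycle 2 | Cycle 3 |
|---|---|---|---|
| 1 | 13 | – | – |
| 2 | 4 | 4 + 5 = 9 | – |
| 3 | 4 | 4 | 5 |

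Early exit and unscheduled visits change individual counts.

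**4. Effect on an any-visit percentage.** The documents give no contact rate and no within-eye correlation, so both are assumed. Let p be a constant per-visit contact rate and ρ the within-eye correlation (beta-binomial model). Then

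P(any contact in n visits) = 1 − ∏ [(1−p)(1−ρ) + iρ] / [(1−ρ) + iρ], for i = 0 to n−1.

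This equals 1 − (1−p)ⁿ at ρ = 0 and p at ρ = 1. With p = 5%:

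| ρ | 4 visits | 9 visits | 13 visits | Ratio 9 vs 4 |
|---|---|---|---|---|
| 0 (independent) | 18.5% | 37.0% | 48.7% | 1.99 |
| 0.3 | 12.7% | 18.9% | 21.8% | 1.48 |
| 0.6 | 8.9% | 11.3% | 12.3% | 1.27 |
| 0.9 | 5.9% | 6.3% | 6.5% | 1.08 |
| 1 (fully persistent) | 5.0% | 5.0% | 5.0% | 1.00 |

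Over p from 2% to 10% and ρ from 0 to 1, the ratio runs from 1.00 to 2.14 for 9 versus 4 visits, 1.00 to 2.98 for 13 versus 4, and 1.00 to 1.24 for 5 versus 4.

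**5. The Week 24 lock.** A two-implant patient who has just reached Week 24 has 2 Cycle 2 looks (Weeks 20 and 24) against 4 in Cycle 1. With p = 5% and independent visits, 1 − 0.95² = 9.8% against 18.5%, a ratio of 0.53. Fully persistent contact again gives 5% against 5%. A one-implant patient at the same point has 4 + 2 = 6 looks in Cycle 1.

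**6. Pooling within a row.** If a fraction f of patients had one implant, the Cycle 1 percentage at Week 52 is (1 − f) × P(4 visits) + f × P(13 visits). The documents do not give f, so the pooled shift cannot be computed.

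**The case against.** The strongest reply is that this is an ordinary descriptive summary. No test or contrast between cycles is planned, and a worst-or-any-in-period summary is common in safety reporting. The same cycle definition governs other ocular safety summaries, so it is a convention of the whole SAP. All of that is true. It limits the harm, but percentages set out by cycle still invite the comparison that their construction does not support.

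Second, the information is not lost. Contact status is listed by patient, and SAP 16.4 says that "all postbaseline assessments will be used for safety evaluation, and all assessments will be presented in the data listings". Persistent and transient contact could be told apart from those listings, but a reader would have to tabulate them by hand. The table shells were not available either: "Specifications of tables, figures, and data listings (TFLs) are contained in a separate document". The absence of a by-visit table is shown for the SAP text only.

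Third, the consequences of contact are covered elsewhere: corneal adverse events of interest overall and by period (SAP 11.1), and graded cell loss by visit and by cycle (SAP 11.3.5). This stands, although neither of them tabulates contact itself.

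Fourth, the large ratios need transient contact, whereas the nonclinical worry is long-lasting contact, for which the ratio is close to 1. The model also holds the contact rate constant although the polymer is expected to degrade within about 12 months (Protocol 1.2), which weakens the 9-visit and especially the 13-visit figures. This stands too. But when contact is persistent, the row still cannot show that it is.

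A reader might infer that the table will make repeat implantation look about twice as risky. The documents do not support that: they give no contact rate, the ratio can be 1.00, and the direction can reverse at the first lock.

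**Conclusion.** The point holds as a weakness in one descriptive safety table. For patients followed to Week 52, the Cycle 1 row mixes 4 and 13 scheduled looks and the Cycle 2 row mixes 4 and 9, so neither has a uniform observation basis and the two cannot be compared. For two-implant eyes the imbalance is 9 looks against 4 in favour of more recorded contact in Cycle 2 at the Week 52 lock, and it can be 2 against 4 the other way at the Week 24 lock. For three-implant eyes the split is 4, 4 and 5, which is nearly balanced.

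The visit counts are firm, given scheduled visits and follow-up to Week 52. The size of the distortion is not: it ranges from none with fully persistent contact to about 2-fold (9 versus 4 visits) with transient contact, under an assumed constant per-visit rate.

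It would be wrong to infer that the noninferiority result is affected or that corneal safety goes unreported. The primary analysis does not use these data, and the corneal adverse event and cell density summaries stand on their own. The change is worth making because it is cheap and the table concerns the safety question that stopped dosing.

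**What to change.** In SAP 11.3.9:

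1. Keep the any-contact row by analysis cycle, but show it by number of implants received (1, 2, 3), with the number of gonioscopy visits contributing to each cell.
2. Add a by-visit table of visible implants and endothelial contact for Bim SR eyes, split by number of implants received to date, using the SAP 16.2 windows.

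A row for contact at consecutive gonioscopy visits is optional. It would speak to persistence, but it also depends on the number of visits and would need the same visit counts beside it.

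The cost is a few more descriptive tables from data already collected, with sparse cells for one-implant and three-implant eyes. Data collection and the primary analysis do not change. If the separate table specifications already contain these rows, a cross-reference in 11.3.9 is enough.
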